4.0 Test Schedule

4.1 Test schedule for Hepatocellular Carcinoma (HCC)

Tests and procedures ¹	Screening ≤21 days prior to registration	Active Monitoring Phase							Obs Clinical follow-up ⁴
		After Reg prior to C1D1 Tx	Cycle 1 Days 8, 15	End of every cycle	End of every 3 cycles (Cycles 1-9) ²	End of every 2 cycles (Cycles 10+) ³	End of treatment	Safety follow-up: 30 days post treatment	
Window			±3 days	±3 days	±7 days	±7 days	±7 days	±7 days	±7 days
History and exam, Wt, PS	X		X	X			X	X	X
Height	X								
Adverse event assessment ⁵	X	X	X	X	X	X	X	X	
Pregnancy test ⁶	X								
Hematology group: CBC /w diff	X ⁷		X	X			X	X	
Chemistry group ⁸	X ⁹		X	X			X	X	
TSH	X			X			X	X	
Ophthalmologic testing ¹⁰	X				X ¹¹	X ¹²			
Nutrition consult ¹³				X					
FGF19 testing ^R			X ¹⁴						
AFP, AFP-L3 % ¹⁵	X				X	X			

Cycle = 21 days ±3 days for Cycles 1-9; Cycle = 42 days ±7 days for Cycles 10+; R= Research funded (See [Section 19.0](#))

¹ All tests and procedures should be performed as needed for clinical care at treating physician's discretion.

² End of Cycles 3, 6, 9 (NOTE: Imaging schedule may be adjusted by treating oncologist as necessary for clinical care.)

³ End of Cycles 11, 13, 15, etc. (NOTE: Imaging schedule may be adjusted by treating oncologist as necessary for clinical care.)

⁴ Observation: every 9 weeks until disease progression, new anti-cancer therapy, death, withdrawal from clinical follow-up, or a maximum of 18 month post registration.

⁵ AEs must be assessed at every cycle; Baseline AE collection for eligibility should be done after patient signs main study consent

⁶ For persons of childbearing potential only: Must be done ≤7 days prior to registration and repeated prior to C1D1 if >7 days between registration and treatment.

⁷ Eligibility requires ≤15 days prior to Registration

⁸ Chemistry: comprehensive metabolic panel (CMP) (80053) plus phosphorus (84100)

⁹ Eligibility requires ≤15 days prior to Registration

¹⁰ Must include external ocular exam; routine slit lamp biomicroscopy of anterior ocular structures include the anterior and posterior chambers; dilation of the pupil with direct/indirect fundoscopy per institutional guidelines; must be done ≤6 months prior to treatment and 2 months after first dose of futibatinib and every 2 months until 6 months after first dose, and every 3 months thereafter and urgently at any time for visual symptoms.

¹¹ Every 2 months for first 6 months and every 3 months until 3 months after last dose of futibatinib; Order at any time if clinically indicated.

¹² Every 3 months until 3 months after last dose of futibatinib; Order at any time if clinically indicated

¹³ Nutrition consult may be done one time at anytime after starting treatment as needed. (This exam is part of expanded patient care.)

¹⁴ Testing may be done on archived tissue at any time after registration – not required to be prior to C1D1 (see [Section 17.0](#))

¹⁵ Performed in all HCC patients at baseline

Tests and procedures ¹	Screening ≤21 days prior to registration	Active Monitoring Phase							Obs Clinical follow-up ⁴
		After Reg prior to C1D1 Tx	Cycle 1 Days 8, 15	End of every cycle	End of every 3 cycles (Cycles 1-9) ²	End of every 2 cycles (Cycles 10+) ³	End of treatment	Safety follow-up: 30 days post treatment	
Clinical tumor genomic testing ¹⁶		X							
Tumor measurement ¹⁷	X ¹⁸				X ¹⁹	X ²⁰	X		X
Tumor biopsy	X ^{21R}								
Research blood specimens ^{22R}		X			X ²³		X		
Research tissue specimens ^{24R}	X						X		
Patient medication diary (Appendix V) ²⁵				X			X		
Patient questionnaire booklets (Appendix VII)		X			X ²⁶		X		

Cycle = 21 days ±3 days for Cycles 1-9; Cycle = 42 days ±7 days for Cycles 10+; R= Research funded (See Section 19.0)

¹⁶ Clinical testing – Note: Molecular analysis including next generation sequencing (NGS) to be done per clinical practice – should be ordered/tested any time prior to end of treatment and results should be uploaded in Medidata Rave® when available

¹⁷ To be performed per Mayo Clinic Cancer Center guidelines – For HCC usually CT chest/abdomen/pelvis or CT chest and MRI abdomen/pelvis; NOTE: If pseudoprogression is suspected at any time, repeat imaging after two more cycles of treatment.

¹⁸ Can be performed ≤28 days prior to registration

¹⁹ To be performed about every 9 weeks (or 3 cycles), ≤7 days prior to planned Day 1 of Cycles 4, and 7 or as clinically indicated

²⁰ To be performed about every 12 weeks, ≤7 days prior to planned Day 1 of Cycles 10, 12, 14 etc., or as clinically indicated

²¹ Research biopsy should be done after registration and prior to treatment on C1D1. Research biopsy may be omitted after discussion with PI, (e.g., if it is not medically feasible, or exceeds lab capacity, or other reason).

²² Research blood specimens to be collected on Cycle 1 Day 1 (or any time between registration and Cycle 1 Day 1), end of Cycle 3 and end of treatment (see [Section 14.0](#))

²³ End of Cycle 3 only

²⁴ Research tissue specimens to be collected during research biopsy any time between registration and prior to treatment on C1D1 (see [Section 17.0](#)). Biopsy can be omitted for patients for whom investigator deems it unsafe.

²⁵ The diary must begin the day the patient starts taking the medication, and must be completed per protocol and returned to the treating institution at each visit.

²⁶ End of Cycle 3, prior to C4 only.

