3.17 Child-Pugh scores of ≤ 7 (Child-Pugh A or B7) (See [Appendix II](#))

3.18 BCLC stage A, B, or C (See [Appendix III](#))

3.19a Negative pregnancy test done ≤ 7 days prior to registration, for persons of childbearing potential only.

3.19b Willing to use an adequate method of contraception (see [Appendix IV](#)) from Registration through 120 days after the last dose of study medication
NOTE: Only for a) persons of childbearing potential or b) persons able to father a child with partners of childbearing potential)

- 3.19c Able to swallow oral medication.
- 3.19d Provide written informed consent.
- 3.19e Willingness to provide mandatory blood specimens for correlative research (see [Section 14.0](#)).
- 3.19f Willingness to provide mandatory tissue specimens for correlative research (see [Section 17.0](#)).
- 3.19g Willingness and the ability to comply with scheduled visits (including geographical proximity), treatment plans, laboratory tests, and other study procedures.
- 3.19h Ability to complete questionnaires by themselves or with assistance.

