3.2 Registration - Exclusion Criteria

- 3.21 Known standard therapy for the patient's disease that is potentially curative or definitely capable of extending life expectancy.
- 3.22 Eligible for first-line treatment with [IMbrave150](#) or [STRIDE](#) regimens.
- 3.23 Any of the following because this study involves an investigational agent whose genotoxic, mutagenic and teratogenic effects on the developing fetus and newborn are unknown:
 - Pregnant persons
 - Nursing persons
 - Persons of childbearing potential who are unwilling to employ adequate contraception
- 3.24 Any of the following prior therapies:
 - Surgery \leq 4 weeks prior to registration
 - Radiotherapy for extended field \leq 4 weeks prior to registration or limited field radiotherapy \leq 2 weeks prior to registration
 - Systemic anticancer therapy \leq 2 weeks prior to registration
NOTE: Prior immunotherapy is allowed unless patient discontinued due to Grade 4 AE
 - Live vaccine \leq 30 days prior to registration
 - Prior treatment with FGFR inhibitor
 - Received strong inhibitors and inducers and sensitive substrates of CYP3A4 \leq 2 weeks prior to registration
 - Received a drug that has not received regulatory approval for any indication as follows:
 - \leq 2 weeks prior to registration for nonmyelosuppressive agents or
 - \leq 4 weeks prior to registration for myelosuppressive agents
- 3.25 History and/or current evidence of any of the following disorders:
 - Retinal or corneal disorder confirmed by retinal/corneal examination and considered clinically significant in the opinion of the Investigator
 - Pneumonitis or interstitial lung disease within \leq 3 years prior to registration
- 3.26 Active CNS metastasis and/or carcinomatous meningitis.
NOTE: Patients with previously treated brain metastases that are clinically and radiologically stable (for at least 4 weeks prior to enrollment) are eligible.

3.27 Corrected QT interval using Fridericia's formula (QTcF) >480 msec.
NOTE: Patients with an atrioventricular pacemaker or other condition (for example, right bundle branch block) that renders the QT measurement invalid are an exception and the criterion does not apply.

3.28 Co-morbid systemic illnesses or other severe concurrent disease which, in the judgment of the investigator, would make the patient inappropriate for entry into this study or interfere significantly with the proper assessment of safety and toxicity of the prescribed regimens.

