6.7 Treatment start

Treatment cannot begin prior to registration and must begin ≤ 7 days after registration.

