Appendix IV Guidelines for Contraception

Your study doctor will discuss prohibited and acceptable birth control methods for use during your participation in this study and for 120 days after the last dose of study drug. These guidelines apply to all persons capable of becoming pregnant or persons capable of fathering a child and their partners of child-bearing potential.

You should notify your study doctor if birth control methods other than those specified below are started during the course of this study or if you start any prescription drug or other medication (including herbal and over-the-counter medications) not prescribed by the study doctor.

One of the two forms of birth control must be highly effective and the second method may also be highly effective or selected from the list of other contraceptive methods.

Highly Effective Methods of Contraception	Progestogen only hormonal contraception associated with inhibition of ovulation (oral, injectable, or implantable)	
	Hormonal methods of contraception including 
 combined oral contraceptive pills (that is, those that contain both estrogen and progestogen) intravaginal (e.g. vaginal ring) transdermal, injectables, implants and intrauterine devices (IUDs) Sometimes, hormonal levels of birth control can be affected by the study drug. Your doctor will tell you whether hormonal forms of birth control are allowed for this study.	
	Non-hormonal IUDs	
	Bilateral tubal occlusion	
	Vasectomized partner	
Less than Highly Effective Methods of Contraception	Complete abstinence	
	Diaphragm with spermicide	
	Cervical cap with spermicide	
	Vaginal sponge with spermicide	
	Progestin only pills	
Unacceptable Methods of Contraception	Male condoms with or without spermicide*	*A male and a female condom must not be used together
	Female Condoms*	
	Periodic abstinence (calendar, symptothermal, post-ovulation methods)	
	Withdrawal (coitus interruptus)	
Spermicide only		
Lactation/amenorrhea method (LAM)		

If you choose abstinence as a method of contraception, your doctor will discuss other methods of contraception with you in the case you choose not to continue abstinence. Pregnancy testing remains mandatory even if you do choose abstinence as your method of contraception. If pregnancy occurs in you or your partner, you must report the pregnancy to the study investigator and agree to be followed for the entire course of pregnancy and birth.

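### The repeat pregnancy test in footnote 6 is triggered only by starts later than Section 6.7 permits, so a compliant patient may begin treatment on a negative test up to 14 days old

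*Combined protocol and SAP*

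**What the plan says.** Four places in the protocol set the timing.

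- Eligibility criterion 3.19a: "Negative pregnancy test done ≤ 7 days prior to registration, for persons of childbearing potential only".
- Section 4.1, footnote 6, on the same test: "Must be done ≤7 days prior to registration and repeated prior to C1D1 if >7 days between registration and treatment".
- Section 6.7: treatment may not precede registration and "must begin ≤ 7 days after registration".
- The pregnancy-test row of the Section 4.1 table has a single mark, under Screening. The column between registration and C1D1 is empty for this row, as are all later columns.

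Three further provisions bear on the point. Footnote 1 leaves additional testing open: "All tests and procedures should be performed as needed for clinical care at treating physician's discretion". Criterion 3.19b requires willingness to use contraception "from Registration through 120 days after the last dose of study medication". Appendix IV tells patients: "Pregnancy testing remains mandatory even if you do choose abstinence as your method of contraception". It names no time point. No section sets a maximum interval between the pregnancy test and the first dose.

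**The concern.** A repeat test before first dose is meant to catch a pregnancy that the screening test was too early to show. Here the condition for repeating it can be met only by a patient who has already departed from Section 6.7. For everyone else the screening result is the only scheduled test, however old it is at C1D1.

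The trigger also counts from the wrong date. It looks at the time since registration, whereas what determines how far a negative result can be relied on is the time since the test.

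Exclusion criterion 3.23 gives the reason this matters: the study involves an agent whose "genotoxic, mutagenic and teratogenic effects on the developing fetus and newborn are unknown". Contraception is required from registration, so it covers the days between registration and C1D1. It does nothing about a conception before registration that the screening test missed. A retest near first dose addresses that remaining risk. The stake is fetal exposure; the efficacy analysis is untouched.

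**Working it through.** The plan states no figure for this interval, so there is none to reproduce. The check is interval arithmetic.

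**Inputs**

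- *a* = days from pregnancy test to registration: 0 to 7 (criterion 3.19a and footnote 6).
- *b* = days from registration to C1D1: 0 to 7 for a compliant start (Section 6.7).
- Age of the result at C1D1 = *a* + *b*.
- Current repeat condition: *b* > 7 (footnote 6).

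**Can a compliant patient meet the condition?** Compliance requires *b* ≤ 7 and the repeat requires *b* > 7. No value satisfies both.

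**Oldest result at first dose.** Maximum of *a* + *b* = 7 + 7 = 14 days.

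**How many permitted combinations exceed 7 days?** There are 8 × 8 = 64 pairs (*a*, *b*).

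| Age at C1D1 (days) | Number of pairs |
|---|---|
| 0 to 7 | 1+2+3+4+5+6+7+8 = 36 |
| 8 to 14 | 7+6+5+4+3+2+1 = 28 |

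The share above 7 days is 28/64 = 43.75%. The footnote retests 0 of the 28.

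**Does the trigger follow the age of the result?**

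| Test day | Start day | Age | Repeat under footnote 6 |
|---|---|---|---|
| day of registration (*a* = 0) | day 8 (*b* = 8, outside 6.7) | 8 days | yes |
| 7 days before (*a* = 7) | day 7 (*b* = 7, compliant) | 14 days | no |

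The older result is the one left alone.

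**Same check with the interval counted from the test.** The condition becomes *a* + *b* > 7. All 28 pairs are retested, and the oldest result that needs no repeat is 7 days. A repeat done at or after registration is itself at most 7 days old at a compliant start. Because *b* > 7 implies *a* + *b* > 7, every late start caught now is still caught.

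**The case against.** The strongest reply is that nothing here is contradictory. All the rules can be followed together, and footnote 6 makes sense as a backstop for starts that slip. Slippage is plausible, because footnotes 21 and 24 place a research biopsy between registration and C1D1. The protocol times screening from registration throughout (laboratory values within 15 days, imaging within 28), and the pregnancy test already has the tightest of these windows. No section says that a 14-day-old result is inadequate, so a limit from test to dose is a new rule. This is fair as to intent: it is a design choice and not an internal contradiction. It does not explain why an 8-day-old result must be repeated when a 14-day-old one need not be.

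Other points limit the scale:

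- The 44% describes a grid. It is a share of patients only if all day pairs are equally likely; depending on site scheduling, the true share could be anywhere from 0% to 100%.
- The group is small. Section 16.83 projects 12 females of 25, so about 12 is the planned ceiling before childbearing potential is considered.
- Appendix IV gives no time point, and the screening test satisfies it. It shows only that contraception is not treated as a replacement for testing.
- Counting from the test is not a complete answer. A patient tested on the day of registration and started on day 7 still gets no retest, nor do the other pairs among the 36. A patient tested 7 days before registration and started on day 1 is retested so soon after registration that a very recent conception could still be missed.
- Other protections exist: unwillingness to use contraception is exclusionary, physicians may test at discretion, and pregnancies are reported and followed. None of these schedules a test before first dose.

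**Conclusion.** The concern holds. For any patient who complies with Section 6.7, the repeat in footnote 6 cannot be triggered, and the only scheduled pregnancy test may be 14 days old at first dose. Both statements follow from the protocol's own limits and need no assumption. The number of patients affected is not given and is probably small; the 28 of 64 figure shows that the gap is not confined to a corner case, and no more than that. No endpoint, sample size or error rate depends on it. The change should be made because it costs little and the fetal effects of the agent are unknown. The documents do not say whether accrual is still open; if it has closed, the correction matters only where this wording is reused.

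**What to change.** In Section 4.1, footnote 6, keep the 7-day screening window and replace the repeat condition with: *repeat before C1D1 if more than 7 days have passed since the most recent negative test*. This uses the interval already in the footnote and changes only the date from which it is counted. Section 6.7 and criterion 3.19a can stay as they are.

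The cost is one line of text and one repeat test for each patient of childbearing potential whose result would be more than 7 days old at C1D1. No extra visit should be needed, since footnote 22 already provides for a research blood draw on C1D1 or between registration and C1D1. A very early conception can still be missed, because a result up to 7 days old is accepted. If the sponsor wants to narrow that further, the stricter option is to retest every patient of childbearing potential at C1D1.

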7.0 Protocol Treatment

7.1 Treatment Schedule

Patients may receive treatment on this trial for up to 2 years until disease progression, unacceptable adverse events, or patient refusal.

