7.11 Treatment medication table – Cycles 1-9

Agent	Dose Level	Route	Day	ReRx
futibatinib	20 mg*	oral	Once daily on Days 1-21	Q3w
pembrolizumab	200 mg	IV	1	Q3w

Cycle length = 21 days ± 3 days

*Investigator may start patients at lower dose (16mg) if clinically indicated (e.g., patient history of diarrhea) after discussion with PI

Once patients have completed Cycle 9, the cycle length can be increased to 6 weeks with imaging every other cycle (~12 weeks).

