11.43 Response Criteria

11.431 Measurement

All target lesions and target lymph nodes followed by CT/MRI/PET-CT/Chest X-ray/physical examination must be measured on re-evaluation at evaluation times specified in [Section 11.1](#). Specifically, a change in objective status to either a PR or CR cannot be done without re-measuring target lesions and target lymph nodes.

Note: Non-target lesions and non-target lymph nodes should be evaluated at each assessment, especially in the case of first response or confirmation of response. In selected circumstances, certain non-target organs may be evaluated less frequently. For example, bone scans may need to be repeated only when complete response is identified in target disease or when progression in bone is suspected.

Note: Pseudoprogression is a term describing an initial increase in tumor burden caused by immune-cell infiltration in the setting of T cell response. This phenomenon is observed in many solid malignancies. This study will allow all patients to continue their assigned therapy after apparent radiographic progression per RECIST v1.1, with close observation (e.g., 4 to 8 week intervals), provided the benefit is judged to be favorable by the investigator and repeat scans in 6 weeks do not show progression per RECIST v1.1. If subsequent imaging studies and/or clinical observations demonstrate that progression in fact has occurred, the date of confirmed progression should be noted as the scan at which the potential progression was first identified.

11.432 Evaluation of Target Lesions

- **Complete Response (CR):** All of the following must be true:
 - a. Disappearance of all target lesions.

- b. Each target lymph node must have reduction in short axis to <1.0 cm.
- c. Normalization of tumor biomarkers.
- o Partial Response (PR): At least a 30% decrease in PBSD (sum of the longest diameter for all target lesions plus the sum of the short axis of all the target lymph nodes at current evaluation) taking as reference the BSD (see [Section 11.41](#)).
- o Progression (PD): At least one of the following must be true:
 - a. At least one new malignant lesion, which also includes any lymph node that was normal at baseline (<1.0 cm short axis) and increased to ≥ 1.0 cm short axis during follow-up.

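### On the optional 42-day cycles, footnote 17 of the test schedule puts the repeat scan for suspected pseudoprogression at nominally 84 days, against 6 weeks in Section 11.431 (minor)

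*Combined protocol and SAP*

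**What the plan says.** Two places in the combined protocol and SAP set the timing of the repeat scan.

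- **Section 4.1, footnote 17** counts in cycles: "If pseudoprogression is suspected at any time, repeat imaging after two more cycles of treatment". It makes no separate provision for the later, longer cycles.
- **Section 11.431** counts in weeks. Treatment may continue past apparent RECIST progression under close observation (4 to 8 weeks is given as an example interval), if the investigator judges the benefit favourable and "repeat scans in 6 weeks do not show progression per RECIST v1.1". If progression is later confirmed, "the date of confirmed progression should be noted as the scan at which the potential progression was first identified".

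Cycles last 21 ± 3 days through Cycle 9. From Cycle 10 they may be lengthened to 42 ± 7 days (Sections 1.6, 7.11 and 7.12). Routine imaging then moves to every second cycle. Footnote 3 lists it as "End of Cycles 11, 13, 15, etc", and footnote 20 says "To be performed about every 12 weeks". Footnotes 1, 3 and 20 leave room for clinical judgement on timing; footnote 1, for example, says "All tests and procedures should be performed as needed for clinical care". On duration, Section 7.1 says "Patients may receive treatment on this trial for up to 2 years".

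**The concern.** A rule written in cycles changes its calendar meaning when the cycle length changes. Two cycles equal the 6 weeks of 11.431 in the 21-day phase, which suggests that the footnote was written for that phase and not revisited when the 6-week option applies.

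The 6-week scan is the safeguard on treating past apparent progression. Section 13.2 otherwise sends a patient with progression to survival follow-up. If a site takes the timing from the test schedule, a patient who may truly be progressing could stay on both drugs for longer than 11.431 allows before anyone looks again. On 42-day cycles the footnote's repeat also coincides with routine imaging, so the special instruction gives no earlier look.

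**Working it through.** **Inputs.** Cycle lengths and windows: Section 4.1. Repeat-scan rules: footnote 17 and Section 11.431. Futibatinib dose: 20 mg daily, lowest level 12 mg (Section 8.1). Pembrolizumab: 400 mg on Day 1 of each 42-day cycle (Section 7.12). Landmark: 27 weeks (Section 16.1). Limit: 2 years, taken as 104 weeks (Section 7.1).

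**The plan's own conversion.** Section 1.6 equates two 42-day cycles with about 12 weeks: 2 × 42 / 7 = 12.0. This reproduces.

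**Footnote 17 in days**

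| Two cycles spanned | Nominal | With cycle windows | Excess over 42 days | Excess over 56 days (8 weeks) |
|---|---|---|---|---|
| 21 + 21 | 42 | 2 × 18 = 36 to 2 × 24 = 48 | 0 | none |
| 21 + 42 | 63 | 18 + 35 = 53 to 24 + 49 = 73 | 21 | 7 |
| 42 + 42 | 84 | 2 × 35 = 70 to 2 × 49 = 98 | 42 | 28 |

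The middle row needs suspicion at about the end of Cycle 8, hence an unscheduled or repeat scan, since routine scans fall at the ends of Cycles 3, 6 and 9. In the last row even the shortest interval, 70 days, exceeds 8 weeks by 14 days.

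**Against the next routine scan.** After the scan before Cycle 10, two more cycles end with Cycle 11, where footnote 3 already places imaging. Section 11.1 gives a flat 9 weeks for re-evaluation; on that reading the footnote's repeat would come after the routine scan.

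**Extra exposure before re-imaging (42 + 42)**

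- Futibatinib: 84 − 42 = 42 days, which is 42 × 20 = 840 mg, or 42 × 12 = 504 mg at the lowest dose level.
- Pembrolizumab: Cycle 10 Day 1 and Cycle 11 Day 1 both precede an end-of-Cycle-11 scan (2 doses). A 6-week scan falls nominally on Cycle 11 Day 1. Only one dose precedes it if it is done and read before that infusion; otherwise there is no difference.

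**Scheduled scans at which the full excess can arise.** Assume 42-day cycles from Cycle 10. The scan before Cycle 10 is at about 9 × 3 = week 27, and later ones follow every 12 weeks: 27, 39, 51, 63, 75, 87, 99. Adding 12 weeks for the footnote's repeat gives 39, 51, 63, 75, 87, 99 and 111. The first six stay within week 104. For the week-99 scan, the 6-week repeat and Cycle 23 Day 1 would both fall at 99 + 6 = week 105, past the limit, so neither the full 42 days nor the extra dose can occur. That leaves six.

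**Primary endpoint.** 27 × 7 = 189 days = 9 × 21 days. Scheduled scans before the landmark therefore fall in the 21-day phase. Of the six affected scans, one is at about week 27 and five are at week 39 or later.

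**Reach.** At the design rates in Section 16.3, 22 × 0.25 = 5.5 to 22 × 0.47 = 10.3, so roughly 6 to 10 evaluable patients would reach the later cycles without progression. Only some would lengthen their cycles, and only some of those would have suspected pseudoprogression. The documents give no rate for it.

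**The case against.** The best defence is that 11.431, not footnote 17, governs treatment past progression. The footnote says when to repeat imaging; it does not authorise dosing. A scan at 6 weeks satisfies 11.431 and nothing in the footnote forbids it, so a site can comply with both. Footnotes 1, 3 and 20 allow earlier imaging. Patients must also return every 42 ± 7 days (Section 7.3), with examination, performance status and laboratory tests at the end of every cycle, and symptomatic deterioration counts as progression (Section 11.45).

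Most of this stands, and it settles the severity. It also rules out two stronger readings. A reader might infer that the plan permits 84 days of treatment past progression without a scan; it does not, because a site doing so would breach 11.431. A reader might also infer that such a patient goes unassessed for 84 days; the visit schedule shows otherwise.

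The defence does not remove the mismatch. The discretion allows an earlier scan without requiring one, and no text says that 11.431 takes precedence over the test schedule. The phrase in footnote 17 extending it to any time also rules out reading it as limited to Cycles 1 to 9.

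**Conclusion.** The point holds as a minor inconsistency. Footnote 17 matches 11.431 only when both cycles are 21 days long. A site that follows the footnote alone on 42-day cycles could exceed 11.431 by up to about 42 days of futibatinib before re-imaging, or by 28 days measured from the 8-week end of the example observation interval. The additional 400 mg pembrolizumab dose is conditional on when the 6-week scan would have been read.

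The count of six scans rests on 42-day cycles from Cycle 10 and a 104-week limit. Sections 13.4 and 13.5 express the limit as 35 cycles and equate that with 2 years, which fits 21-day cycles (35 × 3 = 105 weeks). Counting 35 cycles literally with the longer ones would run to 27 + 26 × 6 = 183 weeks and admit more scans, without changing the excess at each.

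A reader might infer that PFS6 is biased. The documents do not support that: confirmed progression is dated to the first suspicious scan, and all but one of the affected scheduled scans fall well after the landmark. What remains is timing. For suspicion at the week-27 scan, confirmation could come 84 rather than 42 days later, which could leave a late-enrolled patient's status open at an analysis done around 6 months after the last evaluable patient enrols.

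**What to change.** Replace the interval in footnote 17 with: *repeat imaging in 6 weeks (see 11.431), regardless of cycle length, before the next pembrolizumab dose where feasible.*

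Nominal timing in the 21-day phase is unchanged. On 42-day cycles, 6 weeks is one cycle (35 to 49 days with the window) and coincides with a return visit that Section 7.3 already requires. The cost is one wording edit, plus one scan for each of the few affected patients, which 11.431 already calls for. No visit is added, though having the result before infusion may mean imaging a little ahead of Day 1.
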